7.1 Definitions

7.1.1 Adverse Events

An AE is defined as any untoward medical occurrence that occurs during treatment in a patient, but does not necessarily have a causal relationship with their treatment. An AE can therefore be any unfavorable and unintended sign (including an abnormal laboratory finding), symptom, or disease temporally associated with the use of a medicinal product, whether or not the event is considered causally related to the use of the product.

Such an event can result from use of the drug as stipulated in the labeling, as well as from accidental or intentional overdose, drug abuse, or drug withdrawal. Any worsening of a pre-existing condition or illness is considered an AE.

An elective surgery/procedure scheduled to occur during the registry will not be considered an SAE if the surgery/procedure is being performed for a pre-existing condition and the surgery/procedure was planned prior to entry into the registry. However, if the pre-existing condition deteriorates unexpectedly during the registry (e.g., surgery performed earlier than planned) then the deterioration of the condition for which the elective surgery/procedure is being done will be considered an adverse event.

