7.1.2 Adverse Events of Interest

The physician will monitor each patient for clinical and laboratory evidence for adverse events of interest at the Baseline visit and on a routine basis throughout the registry.

Adverse events of interest for this registry include:

- Serious opportunistic infections e.g., invasive fungal infections and TB
- Lymphoma including hepatosplenic T-cell lymphoma; leukemia, non-melanoma skin cancer (NMSC)
- Other malignancies (except lymphoma, leukemia and NMSC)
- Immune reactions including lupus, lupus-like reactions and serious allergic reactions
- Congestive heart failure (CHF)
- Cerebrovascular accident (CVA)
- Myocardial infarction (MI)
- CNS demyelinating disorders (including Multiple Sclerosis and Guillain-Barré syndrome)

- Hepatic events that are serious or lead to permanent discontinuation of Humira (e.g., persistent liver function test abnormalities, acute liver failure and other serious hepatic events)
- Hematologic events that are serious or lead to permanent discontinuation of Humira (e.g., Aplastic anemia, Granulocytopenia, Granulocytes maturation Arrest, Leucopenia, Neutropenia, Pancytopenia and Thrombocytopenia)
- Worsening or new onset of Psoriasis
- Vasculitis
- Diverticulitis
- Intestinal perforation
- Occurrence of symptomatic intestinal obstruction
- Events leading to premature discontinuation of Humira

During the course of the registry additional adverse events of interest may be identified by AbbVie. Updates to the adverse events of interest will be maintained and collected through the eCRF system. Sites will be trained on all updates to the eCRF system.

The physician will assess and record any additional information on the adverse event of interest in detail on the Adverse Events of Interest eCRF.

The physician will assess all reported adverse events of interest for seriousness and follow the requirements/timelines for reporting any AEI that fulfills the criteria of an SAE, as defined in Section [7.1.3](#).

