7.2 Adverse Event Severity

The physician will use the following definitions to rate the severity for any adverse event of interest being collected as an endpoint/datapoint in the registry and for all serious adverse events:

Mild	The adverse event is transient and easily tolerated by the subject.
Moderate	The adverse event causes the subject discomfort and interrupts the subject's usual activities.
Severe	The adverse event causes considerable interference with the subject's usual activities and may be incapacitating or life-threatening.

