7.4 Adverse Event Collection Period

Serious adverse events and adverse events of interest will be reported to AbbVie from the time the physician obtains the subject's initial authorization to use and disclose information (or the subject's informed consent) throughout the patient's participation in the Registry, or direct to HCP process, and/or until 70 days following discontinuation of Humira administration have elapsed (whichever period is longer). A medical event that occurs after a patient discontinues the registry that is considered to be related to the patient's exposure to Humira will be reported via standard post-marketing reporting practices.

In the event Humira therapy is interrupted, SAEs and adverse events of interest will be collected throughout the interruption. If treatment with adalimumab is permanently discontinued for any reason, the reason will be recorded and the patients should be encouraged to remain in the registry for the full 6 years so important safety information can be obtained.

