10.0 Statistical Methods and Determination of Sample Size

10.1 Statistical and Analytical Plans

Analyzable Populations:

Safety Populations During the Registry:

The Registry Safety Population consists of all patients who received at least one dose of Humira (adalimumab) in the Registry. This will be the population for safety analyses in the Registry and include safety data collected during the Registry only.

The "Episodic Dosing" Population will consist of patients in the Registry Safety Population who:

- discontinue Humira (adalimumab) at least once for more than 70 days and receive at least one dose of adalimumab after the treatment interruption,
- do not receive any other biologics during the treatment interruption and,
- provide data before and after Humira (adalimumab) treatment interruption period(s)
- and include safety data collected during the Registry only.

For patients previously treated with commercial Humira before enrollment into the Registry, Day 1 of adalimumab treatment will be the 1st day of Humira therapy, i.e., before enrollment into the Registry. Detailed information on concomitant medications, safety and effectiveness between the 1st dose of Humir and enrollment into the Registry will be available for these patients.

Re-enrollment Safety Population:

The Re-enrollment Safety Population consists of all patients who were discontinued from the Registry due to prior protocol withdrawal criteria (i.e., patients who have discontinued Humira therapy) or discontinued for other reasons and re-consent to participation in the Registry. This will be the population for safety analyses of data collected during the re-enrollment period.

For patients that re-enroll in the Registry, safety information collected between registry discontinuation and re-enrollment based on a retrospective review of their patient records will be analyzed separately.

HCP Safety Population:

The HCP Safety Population consists of all patients that decline re-enrollment to participation in the Registry or who have discontinued from the Registry for other reasons and consent to data release for the completion of a simplified HCP questionnaire in the direct to HCP process. This will be the population for safety analyses of data collected on HCP questionnaire.

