10.5 Safety Analyses

For the Registry Safety Population, treatment-emergent SAEs and adverse events of interest will be summarized. Treatment-emergent SAEs and adverse events of interest are defined as: (1) new events that begin either on or after the first dose of Humira through the last dose of Humira plus 70 days; or (2) increase in severity of ongoing SAEs that had occurred before the first dose date of Humira. The number and percent of patients experiencing SAEs and adverse events of interest will be tabulated by body system and Medical Dictionary for Drug Regulatory Activities (MedDRA[®]) preferred term. The percent of patients will be presented with 95% confidence intervals. In addition, summary of SAEs and adverse events of interest by severity and relationship to registry drug will be presented.

The event rate of SAEs and of each adverse event of interest per 100 patient year of observation will be presented. Event rates will be presented with 95% confidence intervals. For patients enrolled from a prior CD study, the total number of SAEs and adverse events of interest will include the events reported during their participation in the previous study plus any events reports during the Registry.

In addition, Observational AEs: SAEs and AEs of interest occurring from the first dose of Humira in the registry through the last contact including re-enrollment period and during the HCP process will be tabulated.

For the 'Episodic Dosing' Population, following analyses will be provided:

- Summary of SAEs and AEs of special interest will be provided for patients with episodic dosing and without episodic dosing.

- Summary of SAEs and AEs of special interest will be provided before the treatment interruption and after the treatment interruption for patients with episodic dosing.
- For each SAE and AE of special interest, and each episodic dosing, a shift table to summarize number and percentage of patients who have the event or not before the treatment interruption and after the treatment interruption.

For the Re-enrollment Safety Population, the number and percent of patients experiencing SAEs and AEs of interest during the re-enrollment period will be tabulated by body system and MedDRA preferred term. In addition, the number and percent of patients experiencing SAEs and AEs of interest collected between registry discontinuation and re-enrollment based on a retrospective review of their patient records will be tabulated separately.

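### The worsening limb of the treatment-emergent definition names only SAEs, so a non-serious adverse event of interest already on record before the first dose can worsen on Humira and not be counted

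*Protocol*

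**What the plan says.** Section 10.5 opens the definition for both classes of event: "Treatment-emergent SAEs and adverse events of interest are defined as: (1) new events that begin either on or after the first dose of Humira", with the window running "through the last dose of Humira plus 70 days". The alternative route, for events that were already present, is "increase in severity of ongoing SAEs that had occurred before the first dose date of Humira". Adverse events of interest are not mentioned in that second limb.

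Other sections bear on how it works:

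- Section 7.1.2 lists the events of interest. Some carry a seriousness condition (opportunistic infections, allergic reactions) or a seriousness-or-discontinuation condition (hepatic and hematologic events). Others carry none, including vasculitis, diverticulitis, congestive heart failure and "Worsening or new onset of Psoriasis".
- Section 7.1.1 states: "Any worsening of a pre-existing condition or illness is considered an AE".
- Section 7.2 has the physician "rate the severity for any adverse event of interest being collected as an endpoint/datapoint in the registry", as well as for all SAEs.
- Section 7.4 starts event reporting at consent or data authorization, not at first dose. Table 1 schedules safety data collection at enrollment.

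**The concern.** The term being defined has two members, and the worsening limb serves only one of them. The registry deliberately tracks several events of interest whether or not they are serious, and it grades their severity. A counting rule that then ignores a rise in severity for these events discards information already collected.

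At stake are the treatment-emergent counts and percentages, with their 95% confidence intervals, for the Registry Safety Population. Any effect is in one direction: events that got worse on treatment would be missing, and none would be wrongly added.

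**Working it through.** No arithmetic applies, since the point concerns the wording of a definition. The check runs four situations through the two limbs. In each, the patient is newly treated, and the change happens after the first dose and within the treatment-emergent window.

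| Situation | Limb 1 (new event) | Limb 2 (worsening) | Counted? |
|---|---|---|---|
| SAE ongoing before first dose, severity rises | No, not new | Yes | Yes |
| Non-serious event of interest ongoing before first dose, severity rises, same record | No, not new | No, was not an SAE | No |
| Non-serious event of interest ongoing before first dose, becomes serious, same record | No, not new | No, the pre-dose event was not an SAE | No |
| Pre-existing condition worsens and is entered as its own event, dated at the worsening | Yes | Not needed | Yes |

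The second and third rows are the gap. Three questions decide whether it matters.

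**Can a pre-dose event of interest be on record?** Yes. Reporting begins with the patient's "initial authorization to use and disclose information (or the subject's informed consent"), Section 7.1.2 has the physician look for events of interest at the Baseline visit, and Table 1 collects them at enrollment. A newly prescribed patient can have an event recorded before the first injection.

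**Would the worsening be visible in the data?** Yes. Section 7.2 applies the severity scale to events of interest as well as to SAEs.

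**Does another table pick it up?** Not reliably. The Observational AE tabulation in Section 10.5 is wider, running to last contact and including the re-enrollment period and the HCP process. It still counts events occurring from the first registry dose and has no worsening limb.

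Psoriasis needs separate treatment. Because worsening is part of the listed item, and Section 7.1.1 makes worsening of an existing condition an AE, a flare after first dose is naturally an event with its own onset date. It belongs in the fourth row. It moves to the second row only if a site updates the severity of a psoriasis entry made before the first dose.

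**Who is exposed to the gap?** For patients who start on commercial Humira before enrollment, "Day 1 of adalimumab treatment will be the 1st day of Humira therapy, i.e., before enrollment into the Registry", so their registry events fall after first dose. Patients in current sponsor trials are already receiving Humira at entry (Section 6.2.1). What remains is mainly newly prescribed patients, for the interval between consent and first dose.

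**The case against.** The strongest reply is that Section 7.1.1 already solves the problem. If any worsening is itself an AE, and Section 7.0 requires an onset date for each event recorded, then a worsening on treatment is a new event and limb 1 takes it, serious or not. In addition, a chronic condition present before treatment would ordinarily be entered as medical history under Section 6.4.3, and Section 7.1.1 defines an AE as occurring during treatment. Few pre-dose events of interest would then exist. A worsening that leads to hospitalization is reportable as an SAE in its own right, and one that leads to stopping Humira falls under a separate listed item.

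Much of this stands. It disposes of psoriasis as a general example and keeps the reach small. It does not close the gap. Section 7.1.1 says that worsening is an AE, but not that it is a separate record dated at the worsening. Limb 2 itself presupposes events that continue from before the first dose and change in severity. If every worsening became a new event, limb 2 would be unnecessary for SAEs as well. With the limb present for SAEs and silent on events of interest, someone programming the text literally would exclude the latter.

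A reader might go further and infer that worsening psoriasis generally drops out of the main safety tables, or that a sizeable share of psoriasis events is lost. The documents do not support this. It would require sites to date a flare at the original onset of the disease, which the protocol nowhere asks for, and there is no event count from which to derive a share. Nor does the safety background in Section 3.0 name psoriasis among the adverse effects of TNF antagonists, so the protocol gives no basis for calling this the loss of an established class signal. A reader might also infer that the rates per 100 patient-years are affected. The sentence on rates does not itself say treatment-emergent, so that remains an inference.

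**Conclusion.** The definition is wrong as written, at minor severity. Limb 2 is narrower than the term it defines, and a non-serious event of interest on record before first dose that worsens or becomes serious under the same record is excluded from the treatment-emergent summaries. The direction is undercounting only. The number affected is probably small and cannot be estimated, because the protocol gives no count of such events.

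The conclusion rests on two assumptions: that some sites will keep a continuing event as one record and update it, and that the first dose in Section 10.5 means the patient's first Humira dose, as Section 10.1 specifies for patients previously treated with commercial drug.

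**What to change.** In limb 2 of the definition in Section 10.5, insert *or adverse events of interest* after *SAEs*, so that a rise in severity counts for both classes. Severity (Section 7.2) and seriousness (Section 7.1.3) are separate judgements, so also say that a pre-dose event of interest that becomes serious after the first dose counts.

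Add one sentence stating that, consistent with Section 7.1.1, worsening of a pre-existing condition is dated at the worsening. This removes the dependence on how a site chooses to enter a flare.

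The cost is a few words in one section and a matching line in the programming specification. Severity, seriousness and onset dates are already collected, so no new data are needed.

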10.3 Demographics and Registry Enrollment Characteristics

Demographic and Registry enrollment characteristics will be summarized.

The following covariates will be measured to assess their influence on the primary and secondary endpoints: age (years), sex, race/ethnicity, smoking history, duration of CD, severity of CD (as measured by Physician Global Assessment, WPAI and SIBDQ), prior therapies for CD, concomitant CD medications, co-morbid conditions, and adalimumab dosage and exposure duration.

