10.7 Determination of Sample Size

The proposed sample size for this Registry is 5,000 patients. The sample size was calculated based on the following assumptions:

The general population has an expected lymphoma rate of 0.0263 per 100 patient year (PY), based on lymphoma rates in the SEER 17 Registry database for ages 15 to 76²⁰ sex-adjusted to match the Crohn's disease population which is 60% female. Assuming a

lymphoma rate four times higher than the general population rate for Crohn's disease patients previously exposed to IS therapy, 73% of the CD Registry patients would have an expected background rate of 0.1052 per 100 PY, and the remaining 27% of non-IS exposed patients would have an expected background rate of 0.0263 per 100 PY. Therefore, the overall population of patients enrolled in the CD Registry would have an expected background lymphoma rate of 0.084 events per 100 PY (based on the weighted average of the two rates, i.e., $73\% \cdot 0.1052 + 27\% \cdot 0.0263 = 0.084/100 \text{ PY}$).

The Poisson distribution was applied as the appropriate methodology²¹ for the sample size calculation. Based on an event rate of $p_1 = 0.084/100 \text{ PY}$ to allow to reject the null hypothesis H_0 that the observed event rate is more than double the event rate of $0.084/100 \text{ PY}$ ($p_0 = 0.168/100 \text{ PY}$) in favor of the alternative hypothesis H_a with a one-sided type I error rate of $\alpha = 5\%$ and power 90% (type II error $\alpha = 10\%$), the required patient years (n) and events (x_0) would meet the following criteria:

- Type I error

$$\alpha = \sup_{H_0}(P(X \leq x_0)) = P_{p=p_0}(X \leq x_0) = \sum_{k=0}^{x_0} \frac{\exp(-np_0)(np_0)^k}{k!} < 0.05$$

- Power

$$1 - \beta = \inf_{H_a}(P(X \leq x_0)) = P_{p=p_1}(X \leq x_0) = \sum_{k=0}^{x_0} \frac{\exp(-np_1)(np_1)^k}{k!} \geq 0.9$$

- The upper bound of the $100(1-\alpha)\%$ confidence interval for the event rate at given x_0 for the Poisson distribution

$$\frac{\chi_{2(x_0+1); \alpha}^2}{2n} < p_0 = 0.168/100 \text{ PY}$$

The calculation yields that 15,180 total patient years or 17 events will be needed to provide 90% power to detect a doubling of the risk of lymphoma events at one-sided type I error rate of $\alpha = 5\%$.

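### The lymphoma rule that sizes the registry (10.7) is not carried into the analyses, and the event rate planned in 10.5 does not match it in numerator, denominator or interval

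*Protocol*

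**What the plan says.** Section 10.7 takes an "expected background lymphoma rate of 0.084 events per 100 PY" for the enrolled population. It sets the null hypothesis that "the observed event rate is more than double the event rate of" 0.084 per 100 PY, to be rejected "with a one-sided type I error rate of" 5%. It gives the critical-count condition, the power condition and an exact upper-bound criterion against 0.168 per 100 PY. Its result is: "The calculation yields that 15,180 total patient years or 17 events will be needed to provide 90% power". It then projects 16,230 PY from 5,000 patients over six years.

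The analysis sections do not return to this. Section 10.2 plans descriptive statistics. Section 10.3 says "The following covariates will be measured to assess their influence on the primary and secondary endpoints", but no section names a primary endpoint, and the primary objective in 5.0 is long-term safety in general.

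Section 10.5 defines treatment-emergent events as running to 70 days after the last dose, then states: "The event rate of SAEs and of each adverse event of interest per 100 patient year of observation will be presented". Rates carry 95% confidence intervals, with neither sidedness nor method given. For patients from a prior Crohn's disease study, event totals include those from the earlier study. As a separate item, "SAEs and AEs of interest occurring from the first dose of Humira in the registry through the last contact", including the re-enrollment and HCP periods, are to be tabulated. Section 10.1 limits the Registry Safety Population to safety data gathered in the registry. In 7.1.2, lymphoma shares one list item with leukemia and non-melanoma skin cancer (NMSC).

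**The concern.** The sample-size section makes a specific promise: enough follow-up "will be needed to provide 90% power to detect a doubling of the risk of lymphoma events" at a stated error rate. That promise holds only for a rate built as 10.7 builds it, with all lymphomas in a given amount of person-time divided by that same person-time, and a one-sided 95% bound. The rate in 10.5 departs from this in three ways.

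- **Denominator.** Patients are encouraged to stay in the registry, or in the HCP process, after stopping Humira (6.0, 6.3.1, 7.4). Observation time therefore runs past the 70-day event window by design. Dividing windowed events by all observation time biases the rate downwards, towards a false reassurance.
- **Numerator.** Prior-study events are added, against 10.1, with no statement that their patient-years are added too. This biases the rate upwards.
- **Interval.** A 95% interval read in the usual two-sided way is stricter than the one-sided rule in 10.7.

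Lymphoma is the only event for which the protocol sets a quantified question. Section 4.0 describes the registry as a post-marketing commitment and links its extension to six years to the lymphoma rate. A rate reported literally under 10.5 would not have the error rate or power that 10.7 advertises.

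**Working it through.** **Inputs (10.7).** Background p1 = 0.73 × 0.1052 + 0.27 × 0.0263 = 0.0839, stated as 0.084 per 100 PY. Null p0 = 0.168 per 100 PY. One-sided alpha 5%, power 90%, dropout rate 0.231 per year.

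**1. Reproducing the plan.** The rule excludes a doubling when X ≤ x0, where P(X ≤ x0 | n·p0) < 0.05 and P(X ≤ x0 | n·p1) ≥ 0.90.
- n = 15,180, x0 = 17: n·p0 = 25.50, alpha = 0.0499; n·p1 = 12.75, power = 0.904.
- Person-time: 5,000 × (1 − e^(−0.231×6)) / 0.231 = 5,000 × 3.246 = 16,230 PY.

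Both figures reproduce. The sizing arithmetic is sound.

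**2. The rule at 16,230 PY.** n·p0 = 27.27 and n·p1 = 13.63. The critical count is 18, with alpha = 0.040 and power = 0.902. The one-sided 95% upper bound is χ²(0.95; 2(x+1)) / 2n:
- x = 18: 0.1645 per 100 PY, below 0.168, doubling excluded.
- x = 19: 0.1718, not excluded.

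**3. Windowed events over all observation time.** Let f be the share of the 16,230 PY that lies within last dose plus 70 days (assumed; the protocol gives no figure). With a true rate of 0.168, the expected count is 27.27·f, while the rule still allows 18.

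| f | Expected count | P(doubling wrongly excluded) |
|---|---|---|
| 1.0 | 27.27 | 0.040 |
| 0.9 | 24.54 | 0.108 |
| 0.8 | 21.81 | 0.245 |
| 0.7 | 19.09 | 0.462 |

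**4. Prior-study lymphomas added without their patient-years.** The number k is assumed and the true rate is 0.084. Power is P(X ≤ 18 − k | 13.63): 0.902 for k = 0, then 0.852, 0.787 and 0.705 for k = 1, 2 and 3.

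**5. The 95% interval read as two-sided.** The upper bound then uses the 97.5% point.
- 15,180 PY: 17 events give 0.1793, which fails although 10.7 rejects at 17. The largest passing count is 15; power P(X ≤ 15 | 12.75) = 0.785.
- 16,230 PY: 17 passes (0.1677) and 18 fails (0.1753). Power P(X ≤ 17 | 13.63) = 0.852.

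**6. A matched treatment-emergent denominator.** If the patient-years are cut to the event window, the error rate is restored but power changes:
- f = 0.9: 14,607 PY, critical count 16, power 0.883.
- f = 0.8: 12,984 PY, critical count 13, power 0.790.
- f = 0.7: 11,361 PY, critical count 11, power 0.747.

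**The case against.** The best defence is that placing a test and defining its window and denominator is ordinary SAP content, and the SAP is not shown. Section 10.7 already writes out hypotheses, error rate, critical count and upper-bound criterion, and sizing a descriptive registry on a target event is common. The mention of primary endpoints in 10.3 can be read loosely as the safety and effectiveness variables of 6.3.

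Much of this stands. A reader might infer that the protocol has no decision rule, or that an unnamed endpoint alone invalidates it. The text does not support that: the rule is in 10.7, and the wording in 10.3 has no shown effect on a result. What the SAP argument does not cover is what the protocol itself fixes: adding prior-study events in 10.5 conflicts with 10.1, and the rate in 10.5 pairs windowed events with observation time.

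A reader might also set treatment-emergent and observational lymphoma rates against each other and expect opposite conclusions in a large share of registries. The documents do not support that either. Section 10.5 only tabulates the observational events, with no rate or interval. The comparison would also require reading 16,230 PY as on-drug time, whereas 10.7 derives it from time to dropout and calls it follow-up.

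Finally, it is tempting to say that the treatment-emergent window must be primary. That is a trade-off: 4.0 added follow-up after discontinuation to gain safety information, and 3.1 cites events with long latency.

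**Conclusion.** The point holds as a mismatch between 10.7 and 10.5, with the 10.1/10.5 conflict on prior-study events as part of it. The sizing is correct, but the rate as 10.5 words it does not deliver that error rate or power. The more serious direction is false reassurance: 11%, 24% or 46% instead of 4% when 90%, 80% or 70% of observation time lies in the event window. The other two departures cost power: 85% to 71% with one to three added prior-study events at 16,230 PY, and 79% (15,180 PY) or 85% (16,230 PY) under a two-sided reading.

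These are conditional illustrations. The fractions and added counts are assumed, and the departures pull in opposite directions and could partly offset. The false-exclusion figures also rest on reading the rate sentence as using the treatment-emergent events defined just before it. That is the natural reading, since observational events are introduced afterwards as an additional item. A reversed conclusion is possible, not certain; it needs a count near 18 or 19, or substantial observation time outside the window. The change should be made because it is cheap and protects the registry's only quantified question.

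**What to change.** Add one paragraph to 10.5:
- The rule in 10.7 applies to the lymphoma rate, including hepatosplenic T-cell lymphoma and counted separately from leukemia and NMSC.
- A doubling is excluded if the one-sided 95% exact Poisson upper bound is below 0.168 per 100 PY.
- The numerator is registry-only events, consistent with 10.1, and the patient-years come from the same window as the events.
- One window, treatment-emergent or all-observation as the sponsor chooses, is named primary before the counts are known. Section 10.6 foresees periodic cumulative analyses, so this should be settled early.
- The other window, totals with prior-study events and the other adverse events of interest are supportive, with no exclusion claim.

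Section 10.3 should then use the same term for the lymphoma endpoint.

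The cost is wording only; no new data are needed. The sponsor gives up a later choice among counts. If the treatment-emergent window is chosen, its patient-years may fall below 15,180 and the 90% power would have to be restated: about 88%, 79% or 75% if the window covers 90%, 80% or 70% of the planned 16,230 PY.
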